9 SAFETY EVALUATIONS

Safety assessments include adverse events, anaesthetic monitoring and laboratory assessments.

9.1 Definitions

The term “adverse event (AE)” is predominantly used for defining adverse events which occur in connection with medicinal drug product use. The term “adverse event (AE)” may also be used for defining adverse events which occur following the use of a device or following a procedure where the drug or

device is used. Within this protocol, the term “adverse event (AE)” is being used for drug, device or procedural occurrences.

Adverse Event (AE) (Drug)

Any untoward medical occurrence in a subject administered a pharmaceutical product and which does not necessarily have a causal relationship with this treatment. An AE can therefore be any unfavorable and unintended sign (including an abnormal laboratory finding), symptom, or disease temporally associated with the use of an investigational product, whether or not related to the investigational product.

Unless stated otherwise by the investigator, any clinically significant abnormality discovered for a screening assessment required by the protocol will be considered as medical history and not as an AE.

Adverse Event (AE) (Device)

Any untoward medical occurrence, unintended disease, undesired event or injury or any untoward clinical signs (including an abnormal laboratory finding) in subjects/patients, users (healthcare professionals) or other persons whether or not related to the investigational medical device including events related to the investigational device

Device Deficiency

Any inadequacy of an investigational medical device related to its identity, quality, durability, reliability, safety or performance. This may include malfunctions, use error, or inadequacy in the information supplied by the manufacturer.

Procedural events

Any untoward medical occurrence, unintended disease, undesired event or injury or any untoward clinical signs that arises as a result of procedures involved (any procedure in the clinical investigation plan).

For users or other persons, this is restricted to events related to such procedures including anaesthesia, the placement of the fibers or anything else not directly due to the use of the Laser device or drug occurring at the time of the VTP.

Serious Adverse Event (SAE)

Within this protocol, a serious adverse event is any adverse event regardless of causality that meets at least one of the seriousness criteria listed below:

1. Led to a death,

2. Led to a serious deterioration in health that either:
 - resulted in a life-threatening illness or injury, or
 - resulted in a permanent impairment of a body structure or a body function, or
 - required in-patient hospitalization or prolongation of existing hospitalization, or
 - resulted in medical or surgical intervention to prevent life threatening illness or injury or permanent impairment to a body structure or a body function,
3. Led to fetal distress, fetal death or a congenital abnormality or birth defect,
4. Is considered a medically significant event that lead, could have lead, or could lead directly or indirectly to death or severe health impairment of volunteers, users, or other persons if action was not taken to prevent this (including surgical intervention).

NOTE: An SAE may include a report of malfunction of the device such that it has to be monitored more closely or temporarily or permanently taken out of service.

9.2 Adverse Event Monitoring

Any device deficiency that might have led to an SAE if a) suitable action had not been taken or b) intervention had not been made or c) if circumstances had been less fortunate must be reported. Each subject must be carefully monitored for AEs. This also includes abnormal laboratory values. An assessment must be made of the seriousness, severity and relationship to the administration of the study drug and/or the study device(s) and/or the technical procedures of the study. For the purpose of this study, the procedure includes anaesthesia, the insertion, positioning and removing of the catheters and urinary catheterisation of the patient.

The follow-up of patients will be undertaken until 5 years (60 months). It will encompass ALL AEs events occurring during that period, including any occurring after the initiation of additional prostate cancer treatment.

The Investigator is required to question the subject about AEs and intercurrent illnesses since their last visit and must register the information in the subject's medical records. The questions should be generalised and the presence or absence of specific AEs should not be solicited from subjects. The onset and end dates, severity and relationship to study drug must be registered for each AE, as well as outcome, action taken and seriousness (see Section 9.1 for definition).

Subjects experiencing AEs will be monitored by the investigator. All AEs should be followed until satisfactorily resolved or stabilised. Any action taken and follow-up assessments must be recorded in the subject's medical record. Results from follow-up assessments should be filed with the subject's source documentation.

At the end of the study, the investigator will ensure that the end date (if applicable) and any sequelae of all related AE have been fully documented and followed until resolution. If appropriate, the final relationship of AEs to the study drug, device or procedure will be re-assessed. Any ongoing AE, including out of range safety laboratory parameters, will be followed until resolution or no further improvement can be expected. Appropriate action may be taken as judged clinically necessary.

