2 BACKGROUND INFORMATION

2.1 Prostate Cancer: risk stratification and Treatment

Prostate cancer is one of the most common cancers in American men and a leading cause of cancer related suffering and mortality.¹ The incidence in 2012 was estimated at 413,000 new cases in the Americas and over 85,000 deaths. In the European Union, prostate cancer is the most commonly diagnosed cancer in men, and the third cause of cancer-related death.² In 2009, prostate cancer was the second most common cause of cancer-related death in US males and the leading type of cancer in men, with one-third of new cancer cases.³

Tumor stage and Gleason grade, used as the main predictors of risk in prostate cancer, have demonstrated a trend over time toward lower risk disease in US men. Among patients diagnosed with this disease, 46% are reported as being at low risk, 30% at intermediate risk, and 24% at high risk according to the D'Amico classification.^{4,5} The widespread adoption of PSA screening in clinical practice has led to an increased proportion of disease being diagnosed earlier when tumors are smaller and at lower stage^{4,6}, resulting in a very high rate of treatment among younger men and additional societal burden^{7,8}. Despite technological refinements in surgery and radiation therapy, radical whole-gland therapies cause erectile dysfunction in 30-70%, incontinence (requiring pad usage) in 5-10%, and rectal symptoms (diarrhea, bleeding, proctitis) in 5-20% of treated patients.⁹ New forms of conservative management designed to avoid treatment related toxicities have been developed to adapt to this shift toward smaller volume cancers identified at an earlier stage and are now being used in the U.S. and elsewhere, as an alternative to whole gland therapies.^{10,11,12,13,14,15}

These therapies which involve partial gland soft tissue ablation, also called focal therapy, are designed to appropriately address low volume prostate cancer at the proper scale to control the disease while maintaining normal organ function and have become standard therapies at U.S. centers.

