9.3 Documentation of Adverse Events

AE collection will begin after consent has been obtained and continue until the final visit. Every AE or symptom will be recorded in the CRF and will include:

1. nature (brief description)
2. date and time of onset
3. date and time of resolution
4. seriousness (see Section 9.1 for definition)
5. relationship (unrelated, unlikely, possible, probable, or very likely) to the study drug estimated by the investigator
6. if study-related:
 - study drug-related
 - study device-related
 - study technical procedure-related
7. action taken
8. outcome

On the basis of the occurrence and intensity of AEs, coupled with results of any other observations, the Investigator, at his discretion and following discussion with the Sponsor, may decide to withdraw a subject or prematurely end the study for reasons of clinical safety. The date of such termination will be recorded and appropriate treatment instituted at the discretion of the investigator or sub-investigator.

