10.5.1 Analysis of adverse events

Distinctions will be made between the adverse events not related to the study treatment, the technical procedure or the study device, and those related to any of the above.

Numbers and frequencies of AEs will be tabulated and the proportions of patients exhibiting each AE will be displayed. The adverse events will be classified according to the MedDRA nomenclature. The treatment-emergent adverse events (which happen or worsen after the first study drug intake) will be summarised by System Organ Class (SOC) and preferred term. In addition, the adverse events will be classified according to the National Cancer Institute (NCI) Common Terminology Criteria for Adverse Events (CTCAE) which is a safety endpoint of the study. Tabulations will also be made for the System Organ Class (SOC, current MedDRA version), intensity, relationship, seriousness, and attribution corresponding to each AE. Separate tabulations will be made for SAEs.

The treatment-emergent adverse events (which occurred or worsened after the first study drug intake) will be summarised by primary SOC system and preferred term.

For pre-treatment events listings will be provided. For medical/surgical history and additional examinations listings will be provided.

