#### **Initiation of additional therapy**

Additional prostate cancer treatment is defined as any treatment for prostate cancer other than TOOKAD® Soluble-VTP, including surgery, radiotherapy (external beam, brachytherapy, focused), high intensity focused ultrasound, cryotherapy, hormonal therapy for cancer, chemotherapy for cancer.

The time to initiation of therapy will be analyzed using Kaplan-Meier estimates, presented as a survival curve with corresponding 95% confidence intervals. Subjects who did not initiate any therapy will be censored at the time of study termination. The corresponding Kaplan-Meier curve will also be presented. As a sensitivity analysis, this analysis will be repeated excluding ablative therapies and hormonal therapy, that is, an analysis of time to radical therapy (surgery, radiotherapy). Tables and figures will be provided as appropriate.

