#### **Adverse events**

Distinctions will be made between the adverse events not related to the study treatment, related to the study treatment or related to the technical procedure of the VTP. Frequencies of AEs will be tabulated by treatment arm and the proportions of patients exhibiting each AE will be displayed. The adverse events will be classified according to MedDRA version 23.1 or higher.

The treatment-emergent adverse events (adverse events starting after the treatment) will be summarized by System Organ Class (SOC) and preferred term. In addition, the adverse events will be classified according to the NCI Common Terminology Criteria for Adverse Events which is a safety end point of the study. Tabulations will also be made for the System Organ Class, intensity, relationship, seriousness, and attribution corresponding to each AE. Separate tabulations will be made for SAEs.

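### The treatment-emergent window has no end, so the all-cause AE, intensity and SAE tables mix harms of later cancer therapy with those after VTP; tables split at the start of that therapy should be added.

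*Protocol*

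**What the plan says.** **Collection.** Protocol 9.3 states: "AE collection will begin after consent has been obtained and continue until the final visit". Section 9.2 sets the length, "The follow-up of patients will be undertaken until 5 years (60 months", and the scope, "It will encompass ALL AEs events occurring during that period, including any occurring after the initiation of additional prostate cancer treatment". Section 5.5.3 asks that withdrawn men also be followed for safety to the planned end, and section 6.4.11 lets any man have radical therapy at any time.

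**Analysis window.** Protocol 10.5.1 describes "The treatment-emergent adverse events (which happen or worsen after the first study drug intake", and also says "Numbers and frequencies of AEs will be tabulated and the proportions of patients exhibiting each AE will be displayed". The SAP, under Adverse events, says "The treatment-emergent adverse events (adverse events starting after the treatment) will be summarized by System Organ Class (SOC) and preferred term". Each definition has a start and no end. The SAP's Safety analysis section uses the whole safety population. Its only secondary safety analysis is of men retreated at 3 months.

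**Relatedness.** Both analysis sections separate related from unrelated events and plan tabulations by relationship and attribution. Protocol 9.3 has the investigator grade relationship to the study drug on five levels and, where the event is study-related, assign it to drug, device or technical procedure.

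**Later therapy.** The SAP, under Initiation of additional therapy, says "Additional prostate cancer treatment is defined as any treatment for prostate cancer other than TOOKAD® Soluble-VTP, including surgery, radiotherapy"; the list goes on to other ablative, hormonal and cytotoxic treatment.

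**The concern.** A man whose cancer persists after VTP may have a prostatectomy or radiotherapy within the five years. Any erectile, urinary or rectal event that follows starts after VTP, so by definition it is treatment-emergent. It enters the table by organ class and preferred term, the intensity table and, if serious, the SAE table. An all-cause rate built this way depends on how often VTP fails as well as on how well it is tolerated. The mixing falls in the organ systems in which the Protocol background contrasts VTP with radical treatment: section 2.1 says that "radical whole-gland therapies cause erectile dysfunction in 30-70%, incontinence (requiring pad usage) in 5-10"%.

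The SAP has a rule for later radical therapy elsewhere. It is a competing risk, and in a repeat analysis an event, for the biopsy results; it is a failure in the primary analysis when pattern 4 or 5 is found before Month 12; and it has its own time-to-event analysis. The AE tables have no such rule.

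**Working it through.** The plan states no figure on this point, so there is none to reproduce. The check has two parts.

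**1. Which tables are affected**

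- All-cause treatment-emergent AEs by organ class and preferred term: affected, because the window is open-ended and no event is excluded.
- Intensity tables and SAE tables: affected for the same reason. Protocol 9.1 defines an SAE regardless of causality. The exemption in 9.4 covers progression of the cancer, not harms of treating it.
- Related-event tables: not affected if attribution is correct. Three things weaken that protection. No cut-point on the five-level scale defines related. The attribution list has no entry for later cancer therapy. The SAP's split names treatment and technical procedure but not the device, which Protocol 10.5.1 includes.

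**2. How large it could be**

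Inputs:
- N = 50 men to be treated (Protocol synopsis).
- Harm rates h after radical whole-gland therapy (Protocol 2.1): erectile dysfunction 30-70%, incontinence 5-10%, rectal symptoms 5-20%.
- Share s of men who later have radical therapy: not given, so assumed. The values are 5%, 10%, 16.4% (100 − 83.6, non-response at the design rate) and 30% (100 − 70, non-response at the null rate). The last two assume that every non-responder switches.

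Formulas: men switching = N × s; percentage points added to an all-cause rate = 100 × s × h.

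| s | Men switching | Erectile dysfunction, points | Incontinence, points | Rectal symptoms, points |
|---|---|---|---|---|
| 5% | 2.5 | 1.5-3.5 | 0.25-0.5 | 0.25-1.0 |
| 10% | 5 | 3.0-7.0 | 0.5-1.0 | 0.5-2.0 |
| 16.4% | 8.2 | 4.9-11.5 | 0.8-1.6 | 0.8-3.3 |
| 30% | 15 | 9.0-21.0 | 1.5-3.0 | 1.5-6.0 |

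Example: 100 × 0.30 × 0.70 = 21 points, or 50 × 0.30 × 0.70 = 10.5 men.

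For each assumed share these are ceilings. They suppose that no man already has the same event on record and that every harm is reported as an AE. The tables count patients, so overlap reduces the gain to 100 × (1 − b) × s × h, where b is the rate already recorded. With b = 20% (assumed, independent of switching) and s = 30%, erectile dysfunction gains 100 × 0.8 × 0.3 × 0.3 = 7.2 to 100 × 0.8 × 0.3 × 0.7 = 16.8 points, instead of 9-21. Under-reporting lowers this further, since Protocol 9.2 says that specific AEs are not to be solicited.

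**The case against.** The best defence is that the inclusion is deliberate. Section 9.2 says so outright, and section 7.2 takes the same line for the questionnaires, which are meant to reflect all treatments received. This is a coherent treatment-policy view of what happens to men managed with VTP first. It tends to raise the all-cause rates, which is cautious in an unblinded single-arm study. Onset dates are recorded, so a split table could be produced later in any case. The safety objective is descriptive; the passage in section 2.1 about men being spared radical-treatment effects is background and refers to those successfully managed.

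Most of this stands. It shows that complete collection is sound and that the all-events tables should stay. It also tells against making the period before later therapy the main display: that would end follow-up selectively in men whose VTP failed and move their late VTP harms to a lesser table.

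A reader might go further and infer that radical-therapy harms contaminate the VTP adverse event rates as a whole. The documents do not support that. Both plan relatedness and attribution tables, an event caused by a prostatectomy can be recorded as unrelated to VTP, and neither document names the all-cause tables as the main ones. Nor is lack of masking the difficulty in itself, since attributing an event to later surgery requires knowing of the surgery.

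What the defence leaves open is that the separation depends wholly on case-by-case judgement, although a dated split is available. Erectile dysfunction after VTP and then prostatectomy is hard to place with the attribution fields provided.

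**Conclusion.** The point holds for the all-cause treatment-emergent AE, intensity and SAE tables, which will mix harms of later radical therapy with events after VTP. It does not extend to the related-event tables if attribution is correct, and it is no criticism of collecting events to Month 60.

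The size cannot be determined from the documents. The ceiling over the assumed 5-30% switching is 1.5-21 points for erectile dysfunction, at most 3 for incontinence and at most 6 for rectal symptoms. It rests on the Protocol 2.1 rates applying to these men, no overlap and full reporting. The higher values also need every non-responder to switch, and the SAP counts a missing Month 12 biopsy as a failure without implying radical therapy. A share above 30% over five years would raise the ceiling. This is a low-cost improvement to the analysis plan, not a flaw in the trial's conduct.

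**What to change.** Leave collection and the all-events tables as planned. In the SAP, under Adverse events, add with equal prominence treatment-emergent AE and SAE tables in two periods:

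- from VTP to the day before the first additional prostate cancer treatment, as the SAP defines it under Initiation of additional therapy. VTP retreatment is outside that definition, so it stays in this period;
- from that date to the final visit.

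Give the number of men and the person-time in each period. State how an event that begins in the first period and worsens in the second is counted, because the Protocol's definition includes worsening and the SAP's does not. It would also help to say which of the five relationship levels count as related.

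The cost is programming and a few more tables. AE onset dates are already recorded, and the planned time-to-therapy analysis already needs the therapy start dates. The drawback is shorter first-period follow-up in men who switch: late VTP harms in those men fall in the second period, so the two periods must be read together.

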9.3 Documentation of Adverse Events

AE collection will begin after consent has been obtained and continue until the final visit. Every AE or symptom will be recorded in the CRF and will include:

1. nature (brief description)
2. date and time of onset
3. date and time of resolution
4. seriousness (see Section 9.1 for definition)
5. relationship (unrelated, unlikely, possible, probable, or very likely) to the study drug estimated by the investigator
6. if study-related:
 - study drug-related
 - study device-related
 - study technical procedure-related
7. action taken
8. outcome

On the basis of the occurrence and intensity of AEs, coupled with results of any other observations, the Investigator, at his discretion and following discussion with the Sponsor, may decide to withdraw a subject or prematurely end the study for reasons of clinical safety. The date of such termination will be recorded and appropriate treatment instituted at the discretion of the investigator or sub-investigator.

9.4 Serious Adverse Events Reporting

1. AE collection will begin after consent has been obtained and continue until the final visit.
2. All SAEs including laboratory tests abnormalities fulfilling the definition of seriousness and occurring during the clinical trial from the point of signing informed consent to final visit, or within 28 calendar days following the study treatment whichever is the later must be reported immediately (within 2 days of knowledge of the SAE by the Investigator) to the Pharmacovigilance CRO who is in charge of the study pharmacovigilance. A causality assessment will be applied for each event documented. Note that symptoms and signs (such as laboratory abnormalities) that are features of a recognized adverse event should

not be reported separately; i.e. pneumonia which is associated with cough, fever and raised white cell count should only be reported as pneumonia with the signs and symptoms as supporting information.

3. Life-threatening or fatal SAEs regardless of relationship to study drug, study device or study procedure must be reported to the Pharmacovigilance CRO by the investigator (or sub-investigator) within 24 hours of knowledge of the event.
4. The report of an SAE should be made by transmitting the Report Form (as provided in the investigator Site File) to the Pharmacovigilance CRO. The investigator must provide at very least the following information: trial number, subject's initials, date of birth, and patient number, date of treatment, nature of the AE and Investigator's causality assessment (related yes/no to study drug, device or and/or procedure).
5. The report of any SAE must always be confirmed by a written SAE form completed as fully as possible and signed by the investigator. This report must be sent to the Pharmacovigilance CRO within 2 days of the event occurring.
6. The investigator will be informed by the Sponsor of any additional individual national reporting requirements for SAEs applicable in their country and the sponsor will train the investigator to be in compliance with such requirements.
7. The cause of death of a subject in a clinical trial should be reported as an SAE. The only exception is sudden death (when the cause of death is unknown), which is reported as an SAE with death as the outcome.
8. Progression of patient's prostate cancer which is identified as a study end point should not be reported as an SAE unless the investigator assesses that this progression is related to the study procedure or study drug. If any SAE occurs at any point after the study follow-up period, which is considered by the investigator to be related to the study drug or study procedure, this should be reported to the Sponsor/Sponsor representative.
9. If a subject participating in this study requires an extra period of hospitalisation for social reasons either at the start or end of a treatment, this should not be considered a hospitalisation justifying an SAE report.
10. Attendance at hospital that does not require an overnight stay or is for tests only should also not be considered a hospitalisation justifying an SAE report.

Note: medical and scientific judgment should be exercised to decide whether expedited reporting is appropriate in other situations.

All SAE drug reports which meet the reporting criteria will be submitted by the Sponsor to the relevant national or international authorities according to the national regulations, directives and timescales in

force in the different countries where the study is conducted. A separate document will be produced by the Pharmacovigilance CRO which details all reporting requirements.

